Secondary Objectives	To evaluate the impact of rapid identification and AST on antimicrobial utilization and clinical outcomes. 
 • 30-day mortality • Length of stay in the hospital • Days in the ICU • Duration of broad-spectrum gram-negative coverage in the first 72 hours following randomization • Mean time to antibiotic escalation • Mean time to antibiotic de-escalation • Hospital-onset Clostridium difficile • Acquisition of new hospital-acquired infections (HAIs) and/or multidrug resistant organisms (MDROs)
Study Population	All patients with blood culture bottles growing gram-negative bacilli (GNB) detected on Gram staining will be eligible
Number of subjects	500 subjects
Number of sites	2 sites
Clinical Samples	Clinically collected blood cultures with growth of GNB detected by Gram stain
Start of Enrollment:	October 2017
End of Enrollment:	October 2018

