7.2.2 Secondary Outcome Measures

- In-hospital mortality within 30 days of randomization
- Length of stay in the hospital after randomization, up to 30 days, for those patients alive at 30 days. Length of stay will be date of discharge minus date of randomization.
- < 72 hours or ≥72 hours in the ICU after randomization.
- Mean time to antibiotic escalation in those who have antibiotic escalation within 72 hours from randomization. This will be further broken down by whether the escalation was in gram positive coverage, gram negative coverage, or both.
- Mean time to antibiotic de-escalation in those who have antibiotic de-escalation within 72 hours from randomization. This will be further broken down by whether the de-escalation was in gram positive coverage, gram negative coverage, or both.
- Hospital-onset *Clostridium difficile* within 30 days, as defined by the National Healthcare Safety Network (NHSN). This will be normalized to patient-days.²²
- Acquisition of new hospital-acquired infections (HAIs) and/or multidrug resistant organisms (MDROs) within 30 days during index hospitalization identified on routine clinical or surveillance samples. This will be normalized to patient-days. Cultures that will be tracked include the following, from any specimen source, unless otherwise indicated:
 - Methicillin-resistant *Staphylococcus aureus*
 - Vancomycin-resistant *Enterococcus*
 - 3rd generation cephalosporin non-susceptible *Enterobacteriaceae*
 - Carbapenem-resistant *Enterobacteriaceae*, as defined by the CDC: resistant to imipenem, meropenem, doripenem, or ertapenem OR documentation that the isolate possesses a carbapenemase²³
 - Multidrug-resistant *Pseudomonas aeruginosa* (resistant to aminoglycosides, cephalosporins, fluoroquinolones, and carbapenems)²⁴
 - Carbapenem-resistant *Acinetobacter*
 - *Candida* species (isolated from blood cultures only)

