We assume that differences in the primary outcome will be due to the rapid testing results. We anticipate that most subjects will be receiving empiric broad-spectrum antibiotic therapy at randomization, and a difference between the arms of 9 hours or more in time to antibiotic escalation or de-escalation would be reasonable based on the turn-around-time of the rapid test, and clinically relevant with regards to risks of ineffective therapy or prolonged exposure to broad-spectrum agents. Estimates for the SD for time to first modification of antibiotic therapy are based on data from subjects with GNB bacteremia from the BCID trial¹⁵. We assume that the arm including stewardship in the BCID trial (BCID test plus AS), is a reasonable surrogate for the RAPIDS standard testing arm. This is because the BCID test provided minimal susceptibility results for GNB, and did not impact time to antibiotic modifications for subjects with GNB bacteremia¹⁵. Based on the BCID trial data, in the RAPIDS standard testing arm, we expect 63% will have antibiotic de-escalation with mean time of 31 hours (SD 27), 23% will have antibiotic escalation with mean time of 18 hours (SD 21), and 14% will have no antibiotic change. Incorporating the participants with no change, we expect the overall mean time to change in the standard testing arm will be 33.75 hours (SD 28.8). We anticipate that the rapid testing arm will have similar frequencies of antibiotic de-escalation, escalation, and no change. Based on the turn-around-time of the rapid test, we estimate that mean time to antibiotic de-escalation and escalation will be approximately 12 hours (SD 24). Incorporating subjects with no antibiotic change, we expect the overall mean time to antibiotic modification in the rapid testing arm will be

20.4 hours (SD 30.5). The sample size was selected to allow the study to be well powered if this is an optimistic estimate of the standard deviation.

Table 8: Power to detect a difference in means over a range of SD for a sample size of 250 per arm/500 total (200 per arm inflated 20% for death at randomization, comfort care at randomization, GNB bacteremia at same or different institution within 7 days, laboratory errors) for a 2-sided alpha=0.05 test

Difference in means (hours)	SD = 27 h	SD = 30 h	SD = 32 h	SD = 33 h	SD = 34 h
8	84%	76%	70%	68%	65%
9	91%	85%	80%	78%	75%
10	96%	91%	88%	86%	84%
12	99%	98%	96%	95%	94%

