7.4 Analysis

7.4.1 Analysis of primary outcome

We will calculate the mean difference in time to first antibiotic modification within 72 hours post randomization in both treatment arms, together with a 95% confidence interval. Patients who do not have antibiotic modifications will be assigned a time of 72 hours. The primary test will be a t-test (relying on a normal approximation, allowing for unequal variances in the treatment groups) for whether the mean of the primary outcome is different between the arms. We will also carry out a Wilcoxon rank-sum test, to compare the distribution of the time to first antibiotic modification between the arms without the assumption of normality. We will estimate the probability of having an escalation or de-escalation of antibiotics between 0 and 72 hours after randomization using the empirical cumulative distribution function with pointwise 95% confidence intervals.

The primary analysis will be a modified intention to treat analysis (ITT). Participants who died prior to randomization, were on comfort care at randomization as assessed by the study coordinator, had GNB bacteremia at same or different institution within 7 days prior to randomization, or whose blood culture had erroneous Gram stain results in the laboratory will be considered unevaluable. These are all issues which may not be known to the laboratory technologist at the time of randomization and would otherwise be exclusion criteria. Participants randomized to the rapid testing arm will be analyzed as randomized, including cases where the rapid test does not return a result.

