7.4.2 Analysis of secondary and exploratory outcomes

We will compare all secondary and exploratory outcomes between the rapid testing and standard testing arms. Where interest lies in mean differences, we will follow the same approach as for the primary outcome. The DOORs will be compared between arms to estimate the probability (with 95% CI) that a randomly selected participant will have a better DOOR outcome if assigned to rapid testing. We will determine the proportion of very major errors and very major or major errors among patients who receive rapid testing.

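### Mean times to escalation and de-escalation are compared between arms only in patients who had that change, a group formed after randomization; escalation is the sensitive outcome

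*Combined protocol and SAP*

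**What the plan says.** Section 7.2.2 defines two secondary outcomes on patients selected by what happened to them after randomization: "Mean time to antibiotic escalation in those who have antibiotic escalation within 72 hours from randomization" and "Mean time to antibiotic de-escalation in those who have antibiotic de-escalation within 72 hours from randomization". Each is to be split further by gram-positive coverage, gram-negative coverage, or both. The synopsis lists the same two outcomes by short label only.

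Section 7.4.2 makes these between-arm comparisons: "We will compare all secondary and exploratory outcomes between the rapid testing and standard testing arms". On method it adds: "Where interest lies in mean differences, we will follow the same approach as for the primary outcome". In section 7.4.1 that approach is a mean difference with 95% CI, an unequal-variance t-test and a Wilcoxon rank-sum test.

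The primary outcome itself does not select on the event: "Patients who do not have antibiotic modifications will be assigned a time of 72 hours". Section 7.4.1 also plans a cumulative distribution with pointwise 95% CIs: "We will estimate the probability of having an escalation or de-escalation of antibiotics between 0 and 72 hours after randomization".

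**The concern.** Whether a patient is escalated or de-escalated within 72 h is a result of care after randomization, and the rapid test is meant to influence it. The documents show how the event groups could come to differ:

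- Section 1.2 puts standard results at 48-96 h after a culture turns positive. Section 5.2 randomizes at the Gram stain. Some standard-arm changes prompted by susceptibility results may therefore fall after 72 h and drop out of the mean, while the same patients' changes fall inside the window under rapid testing.
- Section 5.3.3 reports any intermediate or resistant result when the two methods disagree, and the treating team is telephoned. Only rapid-arm patients have two methods, so this could produce escalations in that arm alone.

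If the event groups contain different kinds of patients, the difference in event-only means mixes a change in timing with a change in who is counted. At stake is the reading of the two results that give the direction of the antibiotic change behind the primary outcome.

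**Working it through.** **Inputs (section 7.3).** Standard arm: 63% de-escalation, mean 31 h (SD 27); "23% will have antibiotic escalation with mean time of 18 hours (SD 21), and 14% will have no antibiotic change". Rapid arm: similar frequencies, mean about 12 h (SD 24) for either change. 200 evaluable per arm. The shares 63 + 23 + 14 sum to 100%, so I treat them as the shares with each change by 72 h. Section 7.2.2 could count a patient in both directions, so the event counts below rest on this reading.

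**The plan's own figures reproduce.** With no-change patients at 72 h:
- standard arm: 0.63×31 + 0.23×18 + 0.14×72 = 33.75 h
- rapid arm: 0.86×12 + 0.14×72 = 20.4 h

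Power for 9 h with SD 32 and 200 per arm is 80.3% (stated 80%).

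**Planned values, same patients in both event groups.** Expected events per arm are 0.23×200 = 46 escalations and 0.63×200 = 126 de-escalations. The gains are 18 − 12 = 6 h and 31 − 12 = 19 h. Neither reverses.

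**Extra rapid-arm escalations (assumed).** If an extra 5% of rapid-arm patients escalate at time t, the rapid mean is (0.23×12 + 0.05×t)/0.28, to be compared with 18 h. The extra 5% is 5/23, about one fifth of the planned number of escalators.

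| t (h) | Rapid mean (h) | Apparent gain (h) |
|---|---|---|
| 7 | 11.11 | 6.9 |
| 12 | 12.00 | 6.0 |
| 40 | 17.00 | 1.0 |
| 60 | 20.57 | −2.6 |

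**Equal frequencies, different patients (assumed).** Suppose 23% escalate in each arm and nobody who would escalate under either strategy is sped up, but 5% at 40 h are replaced by 5% other patients at 12 h. The rapid mean is (0.23×18 − 0.05×40 + 0.05×12)/0.23 = 11.91 h, an apparent gain of 6.1 h. With SDs 21 and 17.5 and 46 events per arm, SE = √((21² + 17.5²)/46) = 4.03 h. By normal approximation the event-only test would be significant in about 33% of trials. Equal frequencies therefore do not guarantee comparable groups.

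**De-escalation, extreme case (assumed).** Add all 14% no-change patients at 60 h: (0.63×12 + 0.14×60)/0.77 = 20.73 h. A gain of 31 − 20.73 = 10.3 h remains out of 19 h.

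**All-patient mean, 72 h for those without the given change, planned values.**
- De-escalation: 46.17 vs 34.20 h, difference 11.97 h, SE √((29.2² + 34.7²)/200) = 3.20 h, power about 96%.
- Escalation: 59.58 vs 58.20 h, difference 1.38 h, SE √((24.9² + 27.7²)/200) = 2.63 h, power about 8%. The event-only comparison has SE √((21² + 24²)/46) = 4.70 h and power about 25%.

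**What all-patient analyses cannot show.** In the replacement scenario the proportions are 23% vs 23% and the all-patient gain is 0.05×(40 − 12) = 1.40 h. For the planned true speed-up they are 23% vs 23% and 0.23×6 = 1.38 h. The two are practically indistinguishable.

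**Precision of the proportions.** The 95% CI half-width is 1.96×√(2p(1−p)/200): 8.2 points at p = 0.23 and 9.5 points at p = 0.63. Power is about 21% for 23% vs 28% and about 24% for 23% vs 18%.

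**The case against.** The strongest reply is that the plan already covers this. The restriction is stated openly, the outcomes are secondary, and section 7.4.1 plans a 0-72 h cumulative distribution that section 7.4.2 may carry over to these outcomes. This stands in part. If read by direction, the curves would supply much of what is needed. But they are listed under the primary outcome, are not clearly separate by direction, and have no stated between-arm comparison. The event-only means are not labelled descriptive.

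A second reply is that section 7.3 expects similar frequencies. That is a planning assumption, and the replacement scenario shows that equal frequencies do not settle who is being compared. Nor would unequal frequencies prove bias: extra escalations at 12 h leave the 6 h gain unchanged.

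A third reply is that the departures are invented. That is fair: they show sensitivity and predict nothing. The reversal needs extra escalations at 60 h, five times the planned rapid-arm mean.

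Three stronger readings are tempting, and the documents do not support them:
- A reader might infer that the synopsis contradicts section 7.2.2, since it says only "Mean time to antibiotic escalation • Mean time to antibiotic de-escalation". A short label that is silent on the population is not a contradiction.
- A reader might count the missing rule for death or discharge before 72 h as a further defect. In an event-only mean, patients without the change are already outside the average; a rule is needed only once all patients are analyzed.
- A reader might infer that section 7.4.2 brings the 72 h assignment into these outcomes. Within the restricted group it would apply to nobody.

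**Conclusion.** The point holds. The plan specifies a between-arm test in groups formed after randomization, and that comparison can be biased in either direction. The documents do not allow the size or direction to be predicted, so a reader should not infer that these results will be wrong or will favour one arm. With the planned frequencies and times, and the same patients in both groups, there is no reversal.

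Escalation deserves the caution: with about 46 events per arm, plausible-sized shifts in who escalates can remove the planned 6 h gain or create one of similar size. De-escalation is robust over the range examined. The primary outcome keeps all evaluable patients and is unaffected. The figures rest on 200 evaluable per arm, the section 7.3 shares read as exclusive categories, normal approximations, and the assumed departures. This should be fixed, at secondary-outcome level.

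**What to change.** In sections 7.2.2 and 7.4.2, for each direction and for the gram-positive and gram-negative breakdowns, make the between-arm comparison in all evaluable participants:

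1. The proportion with the change by 72 h, as a difference with 95% CI.
2. Separate 0-72 h cumulative incidence curves per arm with pointwise 95% CIs.

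Participants who die or are discharged without the change stay in the denominator as no change. Report the event-only means with the number of events per arm, as description and without a test.

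The all-patient mean with 72 h assigned may be added as a supportive summary, read beside the proportions. It serves well for de-escalation. It should not be the main escalation result, because it has little power there and scores an avoided escalation as 72 h.

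The cost is SAP wording; Appendix I already collects antibiotic administration through 72 h. The downside is imprecision for escalation, with a half-width of about 8.2 points. A non-significant difference in proportions therefore does not show that the event groups are comparable. The change restores a randomized comparison of all patients. It does not identify whether patients were changed earlier or different patients were changed, and the report should not claim that it does.

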7.2.3 Exploratory Analyses

- Standardized costs, obtained from the UHC/Vizient database
- The primary endpoint will be analyzed comparing patients who are:
 - in the ICU at baseline versus not in the ICU at baseline
 - neutropenic at baseline versus not neutropenic at baseline
- The primary endpoint will be analyzed excluding antibiotic modifications made within the first hour after randomization, as these changes may be in response to Gram stain result rather than AXDX result
- 30-day readmission to the index hospital
- The proportion of discrepancies (as detailed in 6.0) between rapid testing and standard of care testing among subjects who receive rapid testing (arm 2)
- Antibiotic intensity score (as detailed in 5.5.3) in the first 72 hours post randomization

- Desirability of outcome response and response adjusted for antibiotic risk within 72 hours (DOOR-RADAR) score (see Table 7 below)

Table 7. Desirability of outcome response (DOOR) ranking table.

DOOR Rank	30-day mortality	In ICU at 72h post-randomization	HO-CDI*	New resistant or hospital-acquired organism**
1	Alive	No	No	No
2	Alive	No	Yes	No
3	Alive	No	No	Yes
4	Alive	No	Yes	Yes
5	Alive	Yes	No	No
6	Alive	Yes	Yes	No
7	Alive	Yes	No	Yes
8	Alive	Yes	Yes	Yes
9	Dead	--	--	--

*HO-CDI, Hospital onset *C. difficile* infection

**Newly acquired within 30 days post-randomization, from clinically collected or surveillance cultures

7.3 Sample Size

The study is designed to detect a difference in primary outcome, mean time to first antibiotic modification in the first 72 hours after randomization. We plan to enroll 500 unique participants (250 in each arm) in order to have at least 200 evaluable participants in each arm. Participants who died prior to randomization, were on comfort care at time of randomization, had GNB bacteremia at same or different institution within 7 days prior to randomization, or who were erroneously randomized due to laboratory issues such as spurious Gram stain result, will be considered unevaluable. This will provide 80% power with a 2-sided alpha=0.05 test, to detect a difference in the time to first modification of antibiotic therapy between the two arms of at least 9 hours, with a standard deviation (SD) of 32 hours. With 500 participants, if the SD is larger than 32 hours, there will still be sufficient power to detect a difference between the arms of 10 or more hours (see Table 8).

We assume that differences in the primary outcome will be due to the rapid testing results. We anticipate that most subjects will be receiving empiric broad-spectrum antibiotic therapy at randomization, and a difference between the arms of 9 hours or more in time to antibiotic escalation or de-escalation would be reasonable based on the turn-around-time of the rapid test, and clinically relevant with regards to risks of ineffective therapy or prolonged exposure to broad-spectrum agents. Estimates for the SD for time to first modification of antibiotic therapy are based on data from subjects with GNB bacteremia from the BCID trial¹⁵. We assume that the arm including stewardship in the BCID trial (BCID test plus AS), is a reasonable surrogate for the RAPIDS standard testing arm. This is because the BCID test provided minimal susceptibility results for GNB, and did not impact time to antibiotic modifications for subjects with GNB bacteremia¹⁵. Based on the BCID trial data, in the RAPIDS standard testing arm, we expect 63% will have antibiotic de-escalation with mean time of 31 hours (SD 27), 23% will have antibiotic escalation with mean time of 18 hours (SD 21), and 14% will have no antibiotic change. Incorporating the participants with no change, we expect the overall mean time to change in the standard testing arm will be 33.75 hours (SD 28.8). We anticipate that the rapid testing arm will have similar frequencies of antibiotic de-escalation, escalation, and no change. Based on the turn-around-time of the rapid test, we estimate that mean time to antibiotic de-escalation and escalation will be approximately 12 hours (SD 24). Incorporating subjects with no antibiotic change, we expect the overall mean time to antibiotic modification in the rapid testing arm will be

20.4 hours (SD 30.5). The sample size was selected to allow the study to be well powered if this is an optimistic estimate of the standard deviation.

Table 8: Power to detect a difference in means over a range of SD for a sample size of 250 per arm/500 total (200 per arm inflated 20% for death at randomization, comfort care at randomization, GNB bacteremia at same or different institution within 7 days, laboratory errors) for a 2-sided alpha=0.05 test

Difference in means (hours)	SD = 27 h	SD = 30 h	SD = 32 h	SD = 33 h	SD = 34 h
8	84%	76%	70%	68%	65%
9	91%	85%	80%	78%	75%
10	96%	91%	88%	86%	84%
12	99%	98%	96%	95%	94%

7.4 Analysis

7.4.1 Analysis of primary outcome

We will calculate the mean difference in time to first antibiotic modification within 72 hours post randomization in both treatment arms, together with a 95% confidence interval. Patients who do not have antibiotic modifications will be assigned a time of 72 hours. The primary test will be a t-test (relying on a normal approximation, allowing for unequal variances in the treatment groups) for whether the mean of the primary outcome is different between the arms. We will also carry out a Wilcoxon rank-sum test, to compare the distribution of the time to first antibiotic modification between the arms without the assumption of normality. We will estimate the probability of having an escalation or de-escalation of antibiotics between 0 and 72 hours after randomization using the empirical cumulative distribution function with pointwise 95% confidence intervals.

The primary analysis will be a modified intention to treat analysis (ITT). Participants who died prior to randomization, were on comfort care at randomization as assessed by the study coordinator, had GNB bacteremia at same or different institution within 7 days prior to randomization, or whose blood culture had erroneous Gram stain results in the laboratory will be considered unevaluable. These are all issues which may not be known to the laboratory technologist at the time of randomization and would otherwise be exclusion criteria. Participants randomized to the rapid testing arm will be analyzed as randomized, including cases where the rapid test does not return a result.

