5.2 Randomization

Patients meeting enrollment criteria will be assigned, in a 1:1 ratio using permuted blocks, to one of the two arms outlined in Section 4.0. The randomization scheme will be stratified by site. Randomization will occur at the time the Gram stain detecting GNB is identified by the lab. Randomization will be performed by the Laboratory Technologists, using an electronic system.

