5.3.2 Standard Subculture and AST

For all patients, the local standard of care for identification and AST of GNB from positive blood cultures will be performed, including standard subculture and AST as well as matrix-assisted laser desorption/ionization mass spectrometry (MALDI-TOF MS). If the primary or AS teams desire to have additional drug susceptibility information that is not routinely reported, they may request this information from the Microbiology Laboratory.

If standard culture methods detect a gram-positive organism, gram-negative cocci, and/or yeast *instead* of a gram-negative organism (as was originally detected on Gram stain), the culture result will be reported in the medical record, as per standard of care, and the subject will be considered unevaluable as he or she will not have GNB bacteremia.

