5.3.4 Antimicrobial Stewardship

All patients in both arms of the study will undergo prospective audit and feedback by the institutional AS programs. The AS physician or pharmacist will review the subject’s microbiology results and medical records. The AS provider will contact the primary service (or the consulting infectious diseases (ID) physician, if applicable) if modifications

to therapy are indicated, at any time following notification of positive Gram stain result, organism identification, and/or AST results. If the ID service is consulting on the subject, the AS team will contact the ID service rather than the primary service. If the rapid test result is ready when the AS team is unavailable (i.e. in the evening or weekend), the AS team will review the record and make recommendations at the beginning of the following working day. Local institutional treatment guidelines will be followed. Recommendations will be communicated to the treating teams via telephone or pager and documented per institutional standards. Recommendation types and acceptance rates will be recorded in the study database. Categories of recommendations include: intravenous to oral conversion, de-escalation of gram negative coverage, de-escalation of gram positive coverage, escalation of gram negative coverage, escalation of gram positive coverage, dose optimization, discontinuation of therapy, therapeutic drug monitoring, reduce/define duration of therapy, ID consultation, and other. More than one stewardship recommendation category may be chosen.

In addition to prospective audit and feedback, other routine institutional AS activities will continue, such as implementation of institutional treatment guidelines, prior authorization of restricted antibiotics, review of all patients on selected antibiotics with feedback to clinicians, and daily review of specific culture results.

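### Randomisation is stratified by site, but the primary t-test and Wilcoxon test use neither site nor any baseline variable, so some precision may be given up

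*Combined protocol and SAP*

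**What the plan says.** Section 5.2 assigns patients 1:1 in permuted blocks and states: "The randomization scheme will be stratified by site". The synopsis gives two sites.

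Section 7.4.1 sets the primary analysis as a difference in means with a 95% CI. Patients without a modification are counted at 72 h. The test is described thus: "The primary test will be a t-test (relying on a normal approximation, allowing for unequal variances in the treatment groups"). It adds: "We will also carry out a Wilcoxon rank-sum test". Neither test has a site term, a stratified form or a covariate, and nothing else in Section 7 supplies one. Section 7.4.2 carries this over to other outcomes: "Where interest lies in mean differences, we will follow the same approach as for the primary outcome".

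Baseline data appear elsewhere. Section 7.2.3 compares the primary endpoint for patients "in the ICU at baseline versus not in the ICU at baseline" and "neutropenic at baseline versus not neutropenic at baseline", as exploratory comparisons rather than adjustment. Section 5.5.1 and Appendix I collect the components of the Pitt Bacteremia Score at baseline.

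**The concern.** When randomisation is balanced within sites, between-site variation cannot contribute to the difference between arms. An unadjusted t-test still counts that variation in its standard error. If the sites differ in mean time to modification, the interval is too wide and the test rejects slightly less than 5% of the time under the null. Baseline variables outside the stratification do not affect the size of the test, but adjusting for those that predict the outcome would narrow the interval.

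The outcome is a care-process time, so a site effect is plausible. For conventional testing, Section 5.3.2 says that "the local standard of care for identification and AST of GNB from positive blood cultures will be performed", and Section 5.3.4 says "Local institutional treatment guidelines will be followed". The documents do not say that the two sites differ, or by how much. At stake is precision. Bias and false-positive risk are not in question.

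**Working it through.** **Inputs from Section 7.3:** difference 9 h, SD 32 h, 200 evaluable per arm, two-sided alpha 0.05. Expected means are 33.75 h (SD 28.8) and 20.4 h (SD 30.5).

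**Assumed, because the documents give no figure:** R², the share of outcome variance explained by the added terms, and the gap in mean outcome between sites.

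**1. The plan's own figure.** SE = 32 × √(2/200) = 3.2 h. Power = Φ(9/3.2 − 1.96) = Φ(0.8525) = 80.3%, which agrees with the stated 80%.

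**2. Effect of adjustment in general.** The SE becomes 3.2 × √(1 − R²), so:
- power = Φ(9/(3.2√(1 − R²)) − 1.96)
- half-width = 1.96 × 3.2 × √(1 − R²)
- equivalent sample size = 400/(1 − R²)

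| Assumed R² | Power | 95% CI half-width | Equivalent patients |
|---|---|---|---|
| 0% | 80.3% | 6.27 h | 400 |
| 5% | 82.3% | 6.11 h | 421 |
| 10% | 84.2% | 5.95 h | 444 |

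**3. Larger SD.** At SD 34 h, where Table 8 shows 75% for 9 h, the noncentral t gives 75.2%, 77.3% and 79.5% for the same three R² values.

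**4. The effect the plan expects.** Difference = 33.75 − 20.4 = 13.35 h. SE = √(28.8²/200 + 30.5²/200) = 2.97 h, so z = 4.50 and power is already 99%. Only the half-width moves: 5.81, 5.67 and 5.52 h.

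**5. Site alone, two equal sites.** R² = (gap/2)²/32². The unadjusted test uses SE 3.2 h while the true SE is 3.2√(1 − R²), so:
- unadjusted power = Φ((9/3.2 − 1.96)/√(1 − R²))
- unadjusted null rejection = 2 × (1 − Φ(1.96/√(1 − R²)))

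| Site gap | R² | Power, unadjusted | Power, site-adjusted | Null rejection, unadjusted |
|---|---|---|---|---|
| 5 h | 0.6% | 80.4% | 80.5% | 4.9% |
| 10 h | 2.4% | 80.6% | 81.3% | 4.7% |
| 14.3 h | 5% | 80.9% | 82.3% | 4.4% |
| 20.2 h | 10% | 81.6% | 84.2% | 3.9% |

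At a 10 h gap the half-width falls from 6.27 h to 6.20 h. With a 70:30 split between sites, R² = 0.3 × 0.7 × gap²/32², and an R² of 5% or 10% needs a gap of 15.6 h or 22.1 h.

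**6. Simulation check.** Two runs, with HC1 and HC3 robust errors, each used 20,000 trials per setting, 400 patients, blocks of 4 within two equal sites and total SD 32 h. The ranges below span the two runs.

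| Site gap | Power, Welch | Power, site-adjusted | Null rejection, Welch |
|---|---|---|---|
| 10 h | 80.2% | 80.7–80.9% | 4.4–4.8% |
| 14.3 h | 80.6–80.7% | 81.8–82.1% | 4.4–4.5% |
| 20.2 h | 81.1–81.3% | 83.6–84.0% | 3.6–4.0% |

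Site-adjusted null rejection was 4.6–5.1% across all gaps. With no gap, adding site changed power by 0.3 points or less. Monte Carlo error is about 0.15 points for null rejection and 0.28 for power, so the simulation supports the formulas but not finer comparisons.

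**The case against.** The strongest reply is that nothing is broken. Under randomisation the unadjusted difference is unbiased, type I error stays at or below 5% and the promised power is met. An unadjusted primary test is a legitimate choice. All of that stands.

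It is also fair that the mismatch with the stratification, taken alone, is nearly harmless. At a 10 h gap, adjusting for site gains about 0.7 points of power and takes under 5 minutes off the half-width. The gains to 82% and 84% need either site gaps of about 14 h and 20 h, both larger than the expected treatment effect of 13.35 h, or prognostic baseline variables whose strength the documents do not give.

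The sites are also less free to differ than the short quotes suggest. Section 5.3.2 names subculture, AST and MALDI-TOF MS for all patients, and Section 5.3.4 requires prospective audit and feedback in both arms. That makes a large site gap less likely but does not rule one out, because conventional testing and treatment guidelines remain local.

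Finally, the fuller fix needs definitions that the plan lacks. It schedules Pitt components rather than a score, and the supplied text gives no neutropenia threshold. This is a real cost. The threshold is needed for the exploratory subgroup in any case.

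**Conclusion.** The point holds as an optional efficiency improvement. Site is used in the randomisation and then dropped from the primary and supporting tests, and baseline severity data are collected but not used in either.

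The certain part is that the terms are absent; any benefit is conditional. With R² between 0% and 10%, adjustment is worth 0 to about 4 points of power at 9 h and SD 32 h, and up to about 0.3 h of half-width. Site alone is worth less than 1 point at gaps up to 10 h. At the plan's expected effect, power does not change materially and only the interval narrows. The gain is most useful if the SD is larger than planned, a risk that Section 7.3 itself raises. At SD 34 h, an R² of 10% would bring 75.2% back to 79.5%.

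**What to change.** In Section 7.4.1, make the primary analysis a linear regression of time to first modification, with the 72 h rule unchanged, on arm and site plus a short fixed list: ICU at baseline (yes/no), neutropenic at baseline (yes/no) and Pitt score (linear). Use heteroscedasticity-robust standard errors, which keep the allowance for unequal variances, and report the adjusted mean difference with its 95% CI. The estimand remains the difference in means. Replace the Wilcoxon test with its site-stratified (van Elteren) form, and keep the Welch t-test as a sensitivity analysis. Section 7.4.2 then inherits the same approach for the secondary mean differences.

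Before any unblinded analysis, fix the covariate coding, the neutropenia threshold, how the Pitt components form a score, and a simple rule for missing covariates, for example replacement by the overall mean with both arms pooled.

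The minimum version adds site only. It avoids the coding decisions, but gains about 1 point of power or less unless the sites differ by well over 10 h.

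The cost is SAP wording and a few lines of code, plus the covariate definitions for the fuller version. No extra patients are needed.
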